8.3 Criteria for Study Permanent Drug Discontinuation

In addition to the criteria for stopping the study drug, the following will constitute criteria for discontinuation of study drug:

1. Development of life-threatening infection or malignancy.
2. Grade 3 or higher neutropenia.
3. Development of clinical depression (see Section 8.5).
4. Acquisition of hepatitis A, B, or C.
5. Pregnancy.
6. If subject's CD4 cell percent remains <14% (see Section 8.2).
7. If it is felt by the site's principal investigator that further participation in the study is no longer in the best interest of the subject.
8. Development of a medical condition, that in the opinion of the investigator, it is in the subject's best interest to discontinue study treatment even if criteria requiring drug discontinuation have not been met.
9. In addition, participants may be withdrawn from the study for:
 - a. Withdrawal of consent
 - b. Non-compliance with study visits or study treatment; subject misses a dose of study drug for reasons other than toxicity
 - c. Termination by sponsor

9 Laboratory Studies

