4.1 Inclusion Criteria

To be eligible for study participation, a volunteer must satisfy all of the following inclusion criteria:

1. Age ≥ 18 years.
2. Documentation of HIV-1 infection by any licensed ELISA test and confirmed by a Western Blot.
3. Receiving a DHHS-approved ARV regimen,.
4. Level of cell-associated HIV RNA ≥ 5 copies/million peripheral blood mononuclear cells (PBMC) done at screening visit 1
5. HIV-1 RNA levels less than detectable by current commercial means (e.g., Roche Amplicor, b-DNA test) for a minimum of 12 months prior to screening at all time points, and with at least 2 measurements in this 12 month window.

6. CD4 ≥ 300 cells/mm³ at pre-entry visit within 14 days prior to enrollment.
7. Ability to sign informed consent and willingness to comply with the study requirements and clinic policies.
8. No evidence of viral hepatitis co-infection as assessed by Hepatitis C antibody, HCV RNA, and hepatitis B surface antigen; determinations at pre-entry visit within 28 days prior to enrollment.
9. No history of or evidence of autoimmune hepatitis or other autoimmune disorders at screening, or antinuclear antibody (ANA $> 3x$ upper limit of normal).
10. Laboratory values at pre-entry visit within 14 days prior to enrollment:
 - Alkaline phosphatase < 2.0 times upper limit of normal
 - Alanine transaminase (ALT) < 2.0 times upper limit of normal
 - Total bilirubin < 2.5 mg/dL (< 40 mg/dL if on Atazanavir)
 - Creatinine clearance ≥ 60 mL/min as estimated by the Cockcroft-Gault equation
 - Neutrophil count ≥ 1500 cells/mm³
 - Platelets $\geq 150,000$ / mm³
 - Hemoglobin ≥ 12.0 mg/dL for men and > 11.0 g/dL for women
 - Fasting glucose < 126 mg/dL
11. No history or evidence of significant clinical depression at screening that in the opinion of the investigator would affect the ability of the patient to participate in the study, or which would constitute a threat for his/her health in case of relapse upon INF treatment. The Beck Depression Inventory score must be ≤ 13 at pre-entry visit.
12. No history of INF/PEG-INF therapy.
13. If capable of pregnancy: use of effective contraception during study: effective contraception methods include abstinence, surgical sterilization of either partner, barrier methods such as diaphragm, condom, cap or sponge, or use of hormonal contraception with an anti-HIV regimen that will not alter metabolism of hormonal contraception.

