5.4 Entry (Day 0)

Participants will have laboratory safety assessments performed and receive their first dose of PEG-IFN. Administration of pegylated interferon will be performed by trained personnel. Vital signs will be obtained, concomitant medications documented, and a targeted physical examination will be performed based upon any signs or symptoms that the subject has experienced since the last visit.

Assessments are detailed in Appendix 1 and include:

- Beck Depression Inventory score
- Complete blood count with differential, platelet count
- Serum chemistries (sodium, potassium, chloride, carbon dioxide, creatinine, urea nitrogen, alkaline phosphatase)
- Urine pregnancy test (women of childbearing age) prior to interferon administration
- ALT, Bilirubin
- Creatinine clearance (Cockcroft-Gault method)
- CD4 count
- Single copy assay for HIV-1 RNA
- HIV-1 RNA standard assay
- Interferon level (baseline)
- PBMCs for storage

5.5 Intensification Phase: Visit 1 (Day 7), Visit 2 (Day 14), Visit 3 (Day 21)

Participants will have laboratory safety assessments performed and receive their subsequent doses of PEG-IFN. Vital signs will be obtained and concomitant medications documented. Administration of interferon will be performed by study personnel. Dosing will be based on body weight obtained during initial evaluation. The last PEG-IFN administration will be on Day 21 (Visit 3). A targeted physical examination will be performed based upon any signs or symptoms that the subject has experienced since the last visit. Assessments are detailed in Appendix 1 and include:

- Beck Depression Inventory score
- Complete blood count with differential, platelet count (STAT, prior to interferon administration)
- Serum chemistries (sodium, potassium, chloride, carbon dioxide, creatinine, urea nitrogen, alkaline phosphatase)
- Creatinine clearance (Cockcroft-Gault method)

- Urine pregnancy test (women of childbearing age) prior to drug administration
- ALT, Bilirubin
- Single copy assay of HIV-1 RNA
- HIV-1 RNA standard assay
- Interferon level

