5.11 Window Periods for Study Visits

The following variable scheduling is permitted for study visits:

Days -58 to 14: ± 1 day

Days 21 to 49: ± 2 days

Days 56 to 84: ± 5 days

Weeks 16 to 48: ± 14 days

6 Concomitant Medications

All concomitant medications will be documented at each study visit.

Concomitant administration of immunomodulatory treatments (including steroids, radiation, IL-2, and anti-neoplastic agents) is not allowed during the course of this trial. Other investigational drugs are excluded. No vaccinations are allowed during the study period from 30 days prior to the time of signing consent to the end of the four week interferon therapy period.

7 Study Drug Administration

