7.3 Dose Modifications/Toxicities

A complete blood count with differential (done STAT) will be reviewed before PEG-INF administration at visits 0, 1, 2, and 3. Participants experiencing an adverse event Grade ≤2 may continue at their current dose. No interferon dose modifications will be made in the study but additional visits or monitoring will be permitted to evaluate participants. Toxicity will be evaluated using the Division of AIDS Table for Grading Adults Adverse Events: (<http://rcc.tech-res.com/safetyandpharmacovigilance/>).

8 Management of Toxicities to Study Drug

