8.2 Toxicity Management

Specific expected toxicities lower than grade 4 will be managed as follows:

Adverse Event Action

Neutropenia	Participants who experience Grade 3 neutropenia will receive filgrastim at 300 µg subcutaneously up to 3 times a week. Absolute neutrophil counts will be monitored until return to subject's baseline or <Grade 1. Patient will be asked to return in 1-3 days for evaluation. If grade 3 neutropenia has resolved, patient will return 2-3 days later for repeat evaluation. If grade 3 neutropenia has not resolved at the day 1-3 visit, additional G-CSF will be administered
-------------	--

and the patient will return daily for evaluation and additional G-CSF as medically indicated until resolved. Filgrastim will be discontinued at this time. Interferon will be continued for Grade 3 neutropenia.

CD4 cell count	If the CD4 count declines to <14%, pneumocystis prophylaxis will be offered until the percentage of CD4 cells increases to ≥14%.
Depression	If a BDS score of 14-19 is reported, assessment by the site investigator will be scheduled before the next dose of study drug. If a BDS score of 20-28 is reported, a psychiatric evaluation is required before the next dose of study drug. If a BDS score is >29 or suicidal ideation is reported, participants will permanently discontinue study drug and undergo prompt psychiatric evaluation.

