9.1 Serum Chemistry and Hematology Profiles

Routine safety laboratory tests (Appendix 1) will be performed to monitor clinical status and detect potential drug-related toxicities. Safety tests will be performed at each site's laboratory. During the intensification phase of the study, results of safety tests will be reviewed by the site investigator at each visit before PEG-Interferon administration.

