9.5 CD4 Counts

CD4 counts (absolute number and percentage) will be measured at Pre-entry, Entry, Visits 1, 4, 8, 9 and the Final Study or Discontinuation Visit. Samples will be processed according to standard flow cytometry procedures.

10 Statistical Considerations

This pilot study will investigate whether pegylated interferon alpha2-b will reduce residual HIV-1 RNA in participants with HIV-1 viremia suppressed below detectable levels as measured by commercial assays. Two relevant questions are: 1) does intensification reduce viremia in a consistent way across different patients, and 2) are there *any* patients in whom intensification reduces viremia? The first question is of primary interest, and it pertains to the population. The second question concerns whether individual intensification responders can be identified. It is possible to find no consistent pattern across patients, yet identify one or more patients in whom the pattern of viremia lowering over time convincingly rules out a flat slope for that patient. Therefore, analyses will be directed at both population responses and individual responses, with the primary emphasis being on the former.

For both population and individual analyses, one complication is that because patients are selected on the basis of low baseline viral loads, regression to the mean would cause subsequent viral loads to be somewhat larger, in the absence of intensification. To account for this, we will use one baseline measurement to determine eligibility and another to assess changes over time.

The primary analysis (which is at the population level), compares the viral loads obtained from the pre-intensification control period to the week 4 value using a paired t-test. A sensitivity analysis will use the nonparametric Wilcoxon signed rank test to analyze these baseline to week 4 changes. Another analysis computes the slope of viral load over time for each patient, and uses a 1-sample t-statistic and confidence interval to estimate and test whether the average slope is 0.

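### The CD4 stopping rule has almost no scheduled CD4 data behind it while interferon is given, and a Beck score of 29 triggers no score-based action

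*Combined protocol and SAP*

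**What the plan says.** Section 8.3 item 6 makes it a ground for permanently stopping study drug that a participant's "CD4 cell percent remains <14% (see Section 8.2"). Section 8.2, to which it points, counts a CD4 decline among the toxicities it expects: "If the CD4 count declines to <14%, pneumocystis prophylaxis will be offered", and the offer lasts until the percentage is back to at least 14%. Neither section says when CD4 is to be repeated, or how many low values make the fall persistent.

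Doses are given on Days 0, 7, 14 and 21. Section 5.5 confirms the end of dosing: "The last PEG-IFN administration will be on Day 21 (Visit 3"). The CD4 schedule appears in three places, which do not agree:

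- Section 5.5, the test list for Days 7, 14 and 21, has no CD4.
- Appendix 1 marks CD4 at Pre-entry 1, Days 0, 28, 56 and 84, and Week 48. Visits 1 to 3 are blank.
- Section 9.5 says that CD4 count and percentage "will be measured at Pre-entry, Entry, Visits 1, 4, 8, 9 and the Final Study or Discontinuation Visit". Visit 1 is Day 7.

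Two general provisions bear on this. Section 7.3 says that "additional visits or monitoring will be permitted to evaluate participants". Section 9.1 says that, during intensification, "results of safety tests will be reviewed by the site investigator at each visit before PEG-Interferon administration".

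Section 8.2 also ties actions to Beck score bands. A score of 14 to 19 needs an investigator assessment, and 20 to 28 a psychiatric evaluation, each before the next dose. A score above 29, or suicidal ideation, means permanent discontinuation and prompt psychiatric evaluation.

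**The concern.** A rule that depends on a percentage *remaining* low needs a first low value and a later one, both early enough to prevent a dose. With four weekly doses, that means CD4 results during the first three weeks. Two of the three schedules provide none, and the third provides one.

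Participant safety is at stake, not the efficacy analysis. Section 14 says the study offers participants no benefit, so its stopping rules should work as written. Under Appendix 1, a participant whose CD4 percentage drops below 14% after the first dose could receive the other three doses with no scheduled result to flag it. Staff following Section 9.5 would have a Day 7 value; staff following Appendix 1 would not.

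The Beck bands raise a smaller point of the same kind: one score has no assigned action, although the scores on either side of it do.

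**Working it through.** No sample size or power figure is involved. The check is a count of samples against doses.

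**Inputs.** Dose days are 0, 7, 14 and 21 (Sections 5.4, 5.5 and 7.1). CD4 days after Day 0 are 28, 56, 84 and 336 under Appendix 1, and 7, 28, 56, 84 and 336 under Section 9.5. Visit windows (Section 5.11) are ±1 day up to Day 14, then "Days 21 to 49: ± 2 days". I assume that a CD4 result is not back before the dose given at the same visit, since Section 5.5 marks only the blood count as STAT.

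**Step 1: CD4 samples after the first dose and up to Day 21.** Appendix 1: 0. Section 9.5: 1 (Day 7).

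**Step 2: second scheduled post-dose value.** Appendix 1: Day 56, which is 56 − 21 = 35 days after the last dose. Section 9.5: Day 28, which is 28 − 21 = 7 days after it.

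**Step 3: do the windows close the gap?** The earliest Day 28 visit is 28 − 2 = Day 26. The latest Day 21 dose is 21 + 2 = Day 23. The Day 28 sample is still at least 26 − 23 = 3 days after the last dose.

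**Step 4: interval with no scheduled CD4.** Appendix 1: 28 − 0 = 28 days. Section 9.5: 28 − 7 = 21 days.

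**Step 5: later doses (Days 7, 14, 21) that item 6 could stop for a new fall on drug.** The plan and the fix must be compared on the same terms. The fix adds CD4 on Days 7 and 14.

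| Terms | Appendix 1 | Section 9.5 | Days 7 and 14 |
|---|---|---|---|
| Scheduled samples only | 0 of 3 | 0 of 3 | 1 of 3 (low on Days 7 and 14, Day 21 stopped) |
| Repeat drawn after a low value; low on Day 7 | 0 of 3 (nothing to prompt it) | 2 of 3 | 2 of 3 |
| Repeat drawn after a low value; first low on Day 14 | 0 of 3 | 0 of 3 | 1 of 3 |
| Fall begins after the Day 14 sample | 0 of 3 | 0 of 3 | 0 of 3 |

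In the second row, the Section 9.5 figure depends on a repeat that Section 7.3 allows but does not require.

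**Step 6: prophylaxis.** One low value is enough. Under Appendix 1, a fall present on Day 7 is first seen on schedule at Day 28, so a Day 7 sample brings the prompt forward by 28 − 7 = 21 days. Section 9.5 already provides that sample.

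**Step 7: Beck bands.** Among whole-number scores of 14 or more, 14–19, 20–28 and 30 upwards each have an action. Only 29 has none.

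**The case against.** The strongest reply is that Section 9.5 is the section devoted to CD4 and should govern. Appendix 1 is incomplete elsewhere: it has no pregnancy test at Visit 3, though Sections 5.5 and 13.2 require one before each dose, and it marks concomitant medications only at Pre-entry 1 and Entry, though Section 6 says every visit. On that reading a Day 7 value exists, can prompt prophylaxis, and can be repeated before Day 14. Confirmatory repeats are ordinarily unscheduled anyway. Section 8.3 items 7 and 8 also let the investigator stop drug at any time.

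Much of this stands. A reader might infer from the scheduled samples that item 6 can stop none of the later doses under either schedule, while the fix rescues two of three. The documents do not support that contrast, because it denies the plan the repeats that it grants the fix. Nor can item 6 be called inoperable for everyone. Eligibility sets a CD4 count of at least 300 "at pre-entry visit within 14 days prior to enrollment" and no percentage. A count of 300 is below 14% once lymphocytes exceed 300/0.14 = 2,143/µL (taking the percentage as a share of lymphocytes). Someone already low could therefore meet item 6 from the Pre-entry and Day 0 values. This shows only that such entry is possible.

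Three things survive the reply. Nothing in the protocol says Section 9.5 overrides Section 5.5 and Appendix 1, and Section 9.1 itself refers to Appendix 1 for the safety tests. The repeat is optional. A fall after Day 7 is unseen on schedule until Day 28 under any version.

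On Beck, a reader might infer that a score of 29 leaves a participant without protection. It does not: suicidal ideation, clinical depression (Section 8.3 item 3) and items 7 and 8 all still apply. Only the score-based trigger is missing. Item 3's reference to a Section 8.5 that does not exist is clerical. The lack of a deadline for scores of 14 to 28 after the last dose is a matter of preference, since those bands gate dosing.

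**Conclusion.** The concern holds as a safety-monitoring defect that should be corrected. Under Section 5.5 and Appendix 1, no scheduled on-drug CD4 can prompt a repeat, a stop or prophylaxis before the last dose. Under Section 9.5, one value can, but stopping on it depends on an optional repeat.

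With repeats allowed on both sides, the gain over Appendix 1 is up to 2 of the 3 later doses stoppable. Over Section 9.5 the gain is narrower: the Day 21 dose for a fall first seen on Day 14, and a required repeat. These figures assume that a repeat result is back before the next dose. They describe what the rule could do, not how many participants would benefit, because the documents do not say how often CD4 percentage falls below 14% over four doses. The Beck gap is a single score, with backstops.

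**What to change.** 1. List CD4 count and percentage at Visits 1 and 2 (Days 7 and 14) in Sections 5.5 and 9.5 and Appendix 1, so that all three agree.
2. Define persistence in Section 8.3 item 6: after any value below 14%, a repeat is required with its result in hand before the next dose, and drug is stopped if the repeat is also below 14%. Offer prophylaxis on the first low value, as Section 8.2 already provides.
3. In Section 8.2, change the top Beck band from >29 to ≥29.

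The cost is two extra CD4 tests per participant against Appendix 1, or one against Section 9.5, at visits that already draw blood, plus a repeat only after a low value. Tube volume is not given. At an assumed 3 to 5 mL per test, two tests use 6 to 10 mL, or 6/550 = 1.1% to 10/550 = 1.8% of the 550 mL ceiling on research blood over 8 weeks (Section 12.1.5). Existing draw volumes are not stated, so the remaining headroom should be checked.

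Turnaround is the practical constraint. At the window limits, dosing visits can be as close as 13 − 8 = 5 days (Day 7 to Day 14) or 19 − 15 = 4 days (Day 14 to Day 21), and both the first result and the repeat must fit. A fall that begins after the Day 14 sample would still first appear at Day 28.

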9.1 Serum Chemistry and Hematology Profiles

Routine safety laboratory tests (Appendix 1) will be performed to monitor clinical status and detect potential drug-related toxicities. Safety tests will be performed at each site's laboratory. During the intensification phase of the study, results of safety tests will be reviewed by the site investigator at each visit before PEG-Interferon administration.

9.2 HIV RNA Levels

HIV-1 RNA levels will be measured by FDA-approved standard assay (b-DNA or HIV RT-PCR assay) and SCA assay will be measured at screening and at each study visit. Samples for b-DNA testing and samples for SCA assay will be processed the same day and plasma will be stored at -80°C. Analysis of HIV in plasma and cells will be analyzed through the Clinical Retrovirology Section of the HIV Drug Resistance Program and the HIV Molecular Monitoring Core (Leidos).

9.3 Pharmacokinetics of Pegylated Interferon

Serum levels of pegylated interferon alpha 2b will be measured at Entry and Visits 1, 2, 3, and 4.

9.4 Peripheral Blood Mononuclear Cells Storage

PBMCs will be collected and stored at Entry, at Visits 4, , and at the Final Visit (13), or in the event of early study discontinuation. Samples will be processed according to standard processing for cryopreservation.

9.5 CD4 Counts

CD4 counts (absolute number and percentage) will be measured at Pre-entry, Entry, Visits 1, 4, 8, 9 and the Final Study or Discontinuation Visit. Samples will be processed according to standard flow cytometry procedures.

10 Statistical Considerations

This pilot study will investigate whether pegylated interferon alpha2-b will reduce residual HIV-1 RNA in participants with HIV-1 viremia suppressed below detectable levels as measured by commercial assays. Two relevant questions are: 1) does intensification reduce viremia in a consistent way across different patients, and 2) are there *any* patients in whom intensification reduces viremia? The first question is of primary interest, and it pertains to the population. The second question concerns whether individual intensification responders can be identified. It is possible to find no consistent pattern across patients, yet identify one or more patients in whom the pattern of viremia lowering over time convincingly rules out a flat slope for that patient. Therefore, analyses will be directed at both population responses and individual responses, with the primary emphasis being on the former.

For both population and individual analyses, one complication is that because patients are selected on the basis of low baseline viral loads, regression to the mean would cause subsequent viral loads to be somewhat larger, in the absence of intensification. To account for this, we will use one baseline measurement to determine eligibility and another to assess changes over time.

The primary analysis (which is at the population level), compares the viral loads obtained from the pre-intensification control period to the week 4 value using a paired t-test. A sensitivity analysis will use the nonparametric Wilcoxon signed rank test to analyze these baseline to week 4 changes. Another analysis computes the slope of viral load over time for each patient, and uses a 1-sample t-statistic and confidence interval to estimate and test whether the average slope is 0.

Secondary analyses will attempt to identify individual intensification responders. One definition of responder is whether the patient had at least a 1-log decrease from baseline to 4 weeks in viral load. Because patients with baseline viral load below 10 cannot achieve this, another method will compute the least squares slope of viral load versus time for each patient and declare patients with statistically significant slopes as responders. Because the goal for this analysis is to summarize the response of a given individual, we treat the data as independent observations from that patient. This is the same assumption made when using a mixed model, namely that conditioned on the random, patient-specific intercept and slope, the observations are independent. For both the 1 log method and significant slope method of identifying individual responders, we attempt to find differences in baseline characteristics between responders and non-responders, though very low power precludes finding any of these statistically significant unless they are huge. Of particular interest is whether baseline viral load predicts responder status. As described above, for this analysis we will use one baseline value to characterize baseline viral load and another for the calculation of slope to identify responder status.

All tests will be two-sided and an alpha level of less than 0.05 will be considered statistically significant. Analyses will be performed on both intent-to-treat and as per protocol participants. Any dropouts and non-adherent participants will be replaced. We do not feel that stopping criteria are necessary as this pilot study is not for prognosis or clinical management; there is no blinding of study treatment and we will be monitoring toxicities in real time. In this study, we will be studying participants on an ongoing basis, and no interim analysis is planned.

11 Sample Size Estimation

This is a pilot study of the effect of pegylated interferon on HIV-1 RNA levels in participants who are receiving antiretroviral therapy. To date, there is limited published data available, and the proportion of participants who will respond with decreases in HIV-1 viral RNA levels remains to be clearly defined. As described above, responses may be similar to those observed with PI, integrase inhibitor, or NNRTI intensification, where no participants have experienced a decrease in viral RNA levels. If so, previous sample size analyses estimating the frequency of suppressible participants are relevant. In the accompanying table, we estimate the 90% confidence intervals of the probability that a participant has a detectable decrease in viral RNA levels (participants suppressed in the table below) after studying increasing numbers of participants without observing episodes of drug suppression. As shown here, if we study 10 participants and observe no

suppression in plasma or cell-associated HIV RNA, we have 90% confidence that the frequency of suppressible participants is less than 21%. For this pilot study, we will request a sample size of 65 participants to achieve our goal of studying 10 participants who have ≥ 0.1 copies/mL HIV-1 RNA at screening.

90% exact confidence intervals (using the Clopper-Pearson method) for the probability of being suppressible.

Participants intensified	Participants suppressed	90% confidence interval
5	0	0,0.45
6	0	0,0.39
7	0	0.0.35
8	0	0,0.31
9	0	0,0.28
10	0	0,0.26
15	0	0,0.18
20	0	0,0.14

12 Hazards/Discomforts/Risks

